8.3.4 Clinical Safety Laboratory Assessments

Refer to Appendix 2 for the list of clinical laboratory tests to be performed and to the SoA for the timing and frequency.

- The investigator or medically qualified designee (consistent with local requirements) must review the laboratory report, document this review, and record any clinically relevant changes occurring during the study in the AE section of the CRF. The laboratory reports must be filed with the source documents. Clinically significant abnormal laboratory findings are those which are not associated with the underlying disease, unless judged by the investigator to be more severe than expected for the participant's condition.
- All protocol-required laboratory assessments, as defined in Appendix 2, must be conducted in accordance with the laboratory manual and the SoA.
- If laboratory values from nonprotocol-specified laboratory assessments performed at the institution's local laboratory require a change in study participant management or are considered clinically significant by the investigator (eg, SAE or AE or dose modification), then the results must be recorded in the appropriate CRF (eg, SLAB).
- For any laboratory tests with values considered clinically significantly abnormal during participation in the study or within 30 days after the last dose of study intervention, every attempt should be made to perform repeat assessments until the values return to normal or baseline or if a new baseline is established as determined by the investigator.

8.3.5 KPS and ECOG Performance Status

The investigator or qualified designee will assess KPS and ECOG performance status at screening (within 10 days prior to randomization). The investigator or qualified designee will assess ECOG performance status on Day 1 of Weeks 1, 3, 5, 9, and Q4W thereafter (Section 1.3). ECOG performance status will also be assessed at the treatment discontinuation visit, and at the 30-day Posttreatment Safety Follow-Up Visit. ECOG performance status [Oken, M. M., et al 1982] will be assessed prior to the administration of the study intervention or study-related procedures.

8.4 Adverse Events, Serious Adverse Events, and Other Reportable Safety Events

The definitions of an AE or SAE, as well as the method of recording, evaluating, and assessing causality of AE and SAE and the procedures for completing and transmitting AE, SAE, and other reportable safety event reports can be found in Appendix 3.

Adverse events, SAEs, and other reportable safety events will be reported by the participant (or, when appropriate, by a caregiver, surrogate, or the participant's legally authorized representative).

The investigator and any designees are responsible for detecting, documenting, and reporting events that meet the definition of an AE or SAE as well as other reportable safety events. Investigators need to document if an SAE was associated with a medication error, misuse, or abuse.

Investigators remain responsible for following up AEs, SAEs, and other reportable safety events for outcome according to Section 8.4.3. The investigator, who is a qualified physician, will assess events that meet the definition of an AE or SAE as well as other reportable safety events with respect to seriousness, intensity/toxicity, and causality.

8.4.1 Time Period and Frequency for Collecting AE, SAE, and Other Reportable Safety Event Information

All AEs, SAEs, and other reportable safety events that occur after the participant provides documented informed consent, but before intervention randomization, must be reported by the investigator if the participant is receiving placebo run-in or other run-in treatment, if the event cause the participant to be excluded from the study, or is the result of a protocol-specified intervention, including, but not limited to washout or discontinuation of usual therapy, diet, or a procedure.

- All AEs from the time of intervention randomization through 30 days after cessation of study intervention must be reported by the investigator.
- All AEs meeting serious criteria, from the time of intervention allocation/randomization through 90 days after cessation of study intervention or 30 days after cessation of study intervention if the participant initiates new anticancer therapy, whichever is earlier, must be reported by the investigator.

Confidential

- All pregnancies and exposure during breastfeeding, from the time of intervention randomization through 30 days for belzutifan or 8 weeks for everolimus following cessation of study intervention, or 30 days after cessation of study intervention if the participant initiates new anticancer therapy must be reported by the investigator.
- Additionally, any SAE brought to the attention of an investigator at any time outside the time specified above must be reported immediately to the Sponsor if the event is considered related to study intervention.

Investigators are not obligated to actively seek AEs or SAEs or other reportable safety events in former study participants. However, if the investigator learns of any SAE, including a death, at any time after a participant has been discharged from the study, and the investigator considers the event to be reasonably related to the study intervention or study participation, the investigator must promptly notify the Sponsor.

All initial and follow-up AEs, SAEs, and other reportable safety events will be recorded and reported to the Sponsor or designee within the time frames as indicated in Table 5.

Type of Event	Reporting Time Period: Consent to Randomization/ Allocation	Reporting TimePeriod:Randomization/AllocationthroughProtocol-specified Follow-up Period	Reporting Time Period: After the Protocol- specified Follow-up Period	Time Frame to Report Event and Follow-up Information to Sponsor
Nonserious Adverse Event (NSAE)	Report if: - due to protocol- specified intervention - causes exclusion - participant is receiving placebo run-in or other run- in treatment	Report all	Not required	Per data entry guidelines
SAE including Cancer and Overdose	Report if: - due to protocol- specified intervention - causes exclusion - participant is receiving placebo run-in or other run- in treatment	Report all	Report if: – drug/vaccine related. (Follow ongoing to outcome)	Within 24 hours of learning of event
Pregnancy/ Lactation Exposure	Report if: – due to intervention – causes exclusion	Report all	Previously reported – Follow to completion/termination; report outcome	Within 24 hours of learning of event
Event of Clinical Interest (require regulatory reporting)	Report if: – due to intervention – causes exclusion	Report – potential drug-induced liver injury (DILI) – require regulatory reporting	Not required	Within 24 hours of learning of event
Event of Clinical Interest (do not require regulatory reporting)	Report if: – due to intervention – causes exclusion	Report – non-DILI ECIs and those not requiring regulatory reporting	Not required	Within 5 calendar days of learning of event

Table 5Reporting Time Periods and Time Frames for Adverse Events and Other
Reportable Safety Events

8.4.2 Method of Detecting AEs, SAEs, and Other Reportable Safety Events

Care will be taken not to introduce bias when detecting AEs and/or SAEs and other reportable safety events. Open-ended and nonleading verbal questioning of the participant is the preferred method to inquire about AE occurrence.

MK-6482-005-09 FINAL PROTOCOL

8.4.3 Follow-up of AE, SAE, and Other Reportable Safety Event Information

After the initial AE/SAE report, the investigator is required to proactively follow each participant at subsequent visits/contacts. SAEs and other reportable safety events, including pregnancy and exposure during breastfeeding, ECIs, cancer, and overdose will be followed until resolution, stabilization, until the event is otherwise explained, or the participant is lost to follow-up (as defined in Section 7.3). The investigator will also make every attempt to follow nonserious AEs that occur in randomized participants for outcome. Further information on follow-up procedures is given in Appendix 3.

8.4.4 Regulatory Reporting Requirements for SAE

Prompt notification (within 24 hours) by the investigator to the Sponsor of SAE is essential so that legal obligations and ethical responsibilities toward the safety of participants and the safety of a study intervention under clinical investigation are met.

The Sponsor has a legal responsibility to notify both the local regulatory authority and other regulatory agencies about the safety of a study intervention under clinical investigation. The Sponsor will comply with country-specific regulatory requirements and global laws and regulations relating to safety reporting to regulatory authorities, IRB/IECs, and investigators.

Investigator safety reports must be prepared for SUSARs according to local regulatory requirements and Sponsor policy and forwarded to investigators as necessary.

An investigator who receives an investigator safety report describing an SAE or other specific safety information (eg, summary or listing of SAEs) from the Sponsor will file it along with the IB and will notify the IRB/IEC, if appropriate according to local requirements.

Note: To meet EU CTR requirements, the Sponsor will report SUSARs to the Eudravigilance database via E2B(R3) electronic ICSR form in compliance with CTR 536/2014.

8.4.5 Pregnancy and Exposure During Breastfeeding

Although pregnancy and infant exposure during breastfeeding are not considered AEs, any pregnancy or infant exposure during breastfeeding in a participant (spontaneously reported to the investigator or their designee), including the pregnancy of a male participant's female partner, that occurs during the study are reportable to the Sponsor.

All reported pregnancies must be followed to the completion/termination of the pregnancy. Pregnancy outcomes of spontaneous abortion, missed abortion, benign hydatidiform mole, blighted ovum, fetal death, intrauterine death, miscarriage, and stillbirth must be reported as serious events (Important Medical Events). If the pregnancy continues to term, the outcome (health of infant) must also be reported.

8.4.6 Disease-related Events and/or Disease-related Outcomes Not Qualifying as AEs or SAEs

Efficacy endpoints as outlined in this section will not be reported to the Sponsor as described in Section 8.4.1.

Specifically, the suspected/actual events covered in this exception include any event that is disease progression of the cancer under study.

8.4.7 Events of Clinical Interest

Selected nonserious and SAEs are also known as ECIs and must be reported to the Sponsor. ECIs that are not SAEs should be collected through 30 days following cessation of study intervention and must be reported by the investigator. ECIs that are SAEs should be collected through 90 following cessation of study intervention and must be reported by the investigator.

Events of clinical interest for this study include:

- a. An overdose of Sponsor's product, as defined in Section 8.5.
- b. Potential DILI events defined as an elevated AST or ALT laboratory value that is greater than or equal to 3X the upper limit of normal and an elevated total bilirubin laboratory value that is greater than or equal to 2X the upper limit of normal and, at the same time, an alkaline phosphatase laboratory value that is less than 2X the upper limit of normal, as determined by way of protocol-specified laboratory testing or unscheduled laboratory testing.*

*Note: These criteria are based upon available regulatory guidance documents. The purpose of the criteria is to specify a threshold of abnormal hepatic tests that may require an additional evaluation for an underlying etiology. The study site guidance for assessment and follow-up of these criteria can be found in the Investigator Study File Binder (or equivalent).

- c. Any ≥Grade 3 anemia
- d. Any ≥Grade 3 hypoxia
- e. Any ≥Grade 3 AE deemed related to belzutifan by the investigator, including laboratory abnormalities

8.5 Treatment of Overdose

Overdose will be defined as any dose greater than 240 mg QD of belzutifan. No specific information is available on the treatment of overdose of belzutifan. In the event of overdose the participant should be observed closely for signs of toxicity. Appropriate supportive treatment should be provided if clinically indicated. Overdose is defined as any dose exceeding the prescribed dose of everolimus. No specific information is available on the treatment of overdose of overdose, everolimus should be interrupted and the participant should be observed closely for signs of toxicity. Appropriate supportive treatment should be provided if clinically indicated.

8.6 Pharmacokinetics

8.7 Pharmacodynamics

Details for the collection, processing, storage, and shipment of samples for the determination of pharmacodynamic effects and biomarker assessments can be found in the study laboratory manual.

8.9 Future Biomedical Research Sample Collection

If the participant provides documented informed consent for FBR, the following specimens will be obtained as part of FBR:

• Leftover specimens as listed in Section 8.8.

8.10 Medical Resource Utilization and Health Economics

Medical resource utilization and health economic data, associated with medical encounters, will be collected in the eCRF by the investigator and study-site personnel for all participants throughout the study. Protocol-mandated procedures, tests, and encounters are excluded.

The data collected may be used to conduct exploratory economic analyses and will include:

• All-cause hospitalizations and emergency department visits, from the time of treatment allocation through 90 days following cessation of study intervention, or 30 days following cessation of study intervention, if the participant initiates new anticancer therapy, whichever is earlier.

8.11 Visit Requirements

Visit requirements are outlined in Section 1.3. Specific procedure-related details are provided in Section 8.

8.11.1 Screening

From -28 days to -1 day prior to randomization, potential participants will be evaluated to determine that they fulfill the entry requirements as set forth in Section 5.

Written consent must be obtained before performing any protocol-specific procedure. Results of a test performed before the participant signing consent as part of routine clinical management are acceptable in lieu of a screening test if performed within the specified time frame.

Screening procedures are to be completed within 28 days before randomization except for the following:

- Laboratory tests are to be performed within 10 days prior to randomization. An exception is HIV (if required by local health authority) and hepatitis testing which may be conducted up to 28 days prior to randomization. Refer to Appendix 7 for country-specific requirements.
- Evaluation of KPS and ECOG is to be performed within 10 days prior to randomization.
- For WOCBP, a urine pregnancy test will be performed within 24 hours prior to randomization. If greater than 1 day has elapsed between the screening pregnancy test and the first dose of study intervention, another pregnancy test (urine or serum) must be performed within 24 hours of first dose and must be negative in order for participants to start receiving study medication. If urine pregnancy results cannot be confirmed as negative, a serum pregnancy test will be required (performed by the local study-site laboratory).

Screening images are to be captured within 28 days prior to randomization.

Participants may be rescreened after initially failing to meet the inclusion/exclusion criteria. Results from assessments during the initial screening period are acceptable in lieu of a repeat screening test if performed within the specified time frame and the corresponding inclusion/exclusion criteria is met. Participants who are rescreened will retain their original screening number.

8.11.2 Treatment Period

Visit requirements are outlined in the SoA (Section 1.3). Specific procedure-related details are provided in Section 8.1. Assessments/procedures should be performed, prior to the administration of study intervention.

8.11.3 Posttreatment

8.11.3.1 Posttreatment Safety Follow-up Visit

The mandatory Safety Follow-up Visit should be conducted approximately 30 days after the last dose of study intervention or before initiation of a new anticancer treatment, whichever comes first.

8.11.3.2 Imaging Follow-up

Participants who discontinue study treatment for reasons other than BICR-verified disease progression should continue with imaging assessments per the protocol-defined schedule

until: 1) disease progression is BICR-verified, 2) initiation of a new anticancer treatment, 3) death, 4) pregnancy, 5) withdrawal of consent, or 6) the end of the study, whichever occurs first. Tumor imaging should be performed Q8W (\pm 7 days) through Week 49, or more frequently if clinically indicated. After Week 49 (\pm 7 days), participants who remain on study intervention will have imaging performed Q12W (\pm 7 days). The imaging visit window is \pm 14 days after Week 109.

8.11.3.3 Survival Follow-up

Participants who experience documented disease progression or start a new anticancer therapy, will move into the Survival Follow-up Phase and should be followed for survival (in-person visit, telephone contact, medical record review, etc.) approximately Q12W. Every effort should be made to assess for survival status until death, withdrawal of consent, or the end of the study, whichever occurs first. Information regarding initiation of a new anticancer treatment will also be collected.

The first survival follow-up assessment should be scheduled as described below:

For participants who discontinue treatment intervention and who will not enter Efficacy Follow-up, the first survival follow-up contact will be scheduled 12 weeks after the Discontinuation Visit and/or Safety Follow-up Visit (whichever is last).

For participants who completed assessments in Efficacy Follow-up, the first survival followup contact will be scheduled 12 weeks after the last efficacy assessment follow-up visit has been performed.

To ensure current and complete survival data are available at the time of database locks, updated survival status may be requested during the course of the study by the Sponsor. For example, updated survival status may be requested prior to, but not limited to an IA and/or FA. Upon Sponsor notification, all participants who do not/will not have a scheduled study visit or study contact during the Sponsor defined time period will be contacted for their survival status.

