Abbreviations: AE = adverse event; aPTT = activated partial thromboplastin time; β -hCG = β -human chorionic gonadotropin; BICR = blinded independent central review; CBC = complete blood count; CR = complete response; CT = computed tomography; **C**C = discontinuation; ECG = electrocardiogram; ECOG = Eastern Cooperative Oncology Group; EORTC QLQ-C30 = European Organisation for the Research and Treatment of Cancer Quality of Life Questionnaire 30; EOT = end-of-treatment; EQ-5D-5L = EuroQoL-5 dimensions-5 levels; FKSI-DRS = Functional Assessment of Cancer Therapy – Kidney Symptom Index-disease-related symptoms; HBV = hepatitis B virus; HBsAg = Hepatitis B surface antigen; HCV = hepatitis C virus; HIV = human immunodeficiency virus; ICF = informed consent form; ID = identification; INR = International normalized ratio; KPS = Karnofsky performance status; MRI = magnetic resonance imaging; PK = pharmacokinetics; PRO = patient-reported outcome; PT = prothrombin time; Q4W = every 4 weeks; Q8W = every 8 weeks; Q12W = every 12 weeks; Q16W = every 16 weeks; QD = once daily; QoL = quality of life; RCC = renal cell carcinoma; RECIST = Response Evaluation Criteria in Solid Tumors; RNA = ribonucleic acid; SAE = serious adverse event; SoA = schedule of activities; Wk = week; WOCBP = women of childbearing potential.

- a. Week 1 Day 1 denotes the first dose of study treatment, which should be on the date of randomization, but can be within 3 days following randomization. Every effort should be made to ensure the participants receive the first dose of study intervention on the day of randomization.
- b. Clinic visits after Week 13 are Q4W.
- c. Long-term follow-up may be accomplished via an in-person visit, contact, medical record review, etc. Participant status information includes survival status and subsequent antineoplastic therapies for RCC.

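### For participants who stop at BICR-verified progression and start no new therapy, SAEs, serious ECIs and hospitalizations are due through day 90, but nothing in the schedule prompts for them after the day-30 safety visit

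*Protocol*

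**What the plan says.** **What must be collected.** Protocol Section 8.4.1 requires "All AEs meeting serious criteria, from the time of intervention allocation/randomization through 90 days after cessation of study intervention", shortened to "30 days after cessation of study intervention if the participant initiates new anticancer therapy, whichever is earlier". Section 4.1 and the AE-monitoring note in the Schedule of Activities (SoA, Section 1.3) repeat this. Section 8.4.7 adds that "ECIs that are SAEs should be collected through 90 following cessation of study intervention"; the unit is missing, but days is plainly meant. Section 8.10 collects all-cause hospitalizations and emergency department visits "from the time of treatment allocation through 90 days following cessation of study intervention", with the same new-therapy exception as Section 8.4.1.

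**When participants are seen.** The SoA sets the Safety Follow-up Visit at 30 days after the last dose, with a window of +7 days. Under Section 8.2.1.3, a participant who stops because of BICR-verified progression needs no imaging after the end-of-treatment scan. Section 8.11.3.2 keeps imaging follow-up for those who stop for other reasons. For a participant who does not enter efficacy follow-up, Section 8.11.3.3 states that "the first survival follow-up contact will be scheduled 12 weeks after the Discontinuation Visit and/or Safety Follow-up Visit (whichever is last". The SoA gives survival contacts a window of ±7 days.

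**What is asked.** The AE-monitoring row of the SoA is marked at discontinuation, Safety Follow-up and Imaging Follow-up, and is blank under Survival Follow-up. The row for subsequent antineoplastic therapy, by contrast, is marked under Survival Follow-up. Footnote c describes the content of long-term follow-up: "Participant status information includes survival status and subsequent antineoplastic therapies for RCC".

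**The concern.** The collection window and the visit calendar do not fit together for participants who stop at verified progression, which is one of the protocol's main stopping rules. Section 8.4.2 prefers questioning the participant as the way to detect events. For this group no questioning is scheduled between the safety visit and the end of the window, and the first contact afterwards has no AE mark. A site that follows the SoA exactly would never ask about most of a period the protocol says must be covered.

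At stake is the completeness of non-fatal SAE and hospitalization data from about day 31 to day 90. These data feed the SAE summaries, including the Tier 2 comparison of SAEs reaching 5% in either arm (Protocol Section 9.6.2, SAP Section 3.6.2), and the exploratory economic analyses. Participants who stop for other reasons do have AE monitoring marked at their imaging follow-up visits, so the same window is handled differently according to why treatment stopped.

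**Working it through.** The plan states no figure to reproduce; this is calendar arithmetic on its own offsets.

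**Inputs**
- Collection window: day 90 after cessation, if no new anticancer therapy is started (8.4.1, 8.10).
- Safety Follow-up Visit: day 30 to day 37 (SoA).
- First survival contact: 12 weeks = 84 days after the later of the discontinuation and safety visits (8.11.3.3), ±7 days (SoA).
- Assumptions: cessation is the day of last dose, the safety visit is the later of the two visits, and efficacy follow-up in 8.11.3.3 means the SoA's imaging follow-up.

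**Date of the first survival contact**
- Without the ±7-day window: 30 + 84 = day 114 to 37 + 84 = day 121.
- Earliest with the window: 30 + 84 − 7 = day 107.
- Latest with the window: 37 + 84 + 7 = day 128.
- Past the end of collection: 107 − 90 = 17 days to 128 − 90 = 38 days.
- If the discontinuation visit comes after the safety visit, the contact can be later still.

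**Part of the window with no scheduled prompt**
- Safety visit on day 30: 90 − 30 = 60 days; 60/90 = 67%.
- Safety visit on day 37: 90 − 37 = 53 days; 53/90 = 59%.

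**Could the visit windows close the gap?** For the contact to fall by day 90 even at its earliest, the safety visit would have to be on or before day 90 − 84 + 7 = 13. The SoA places it no earlier than day 30.

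**Comparison with participants who stop for other reasons.** Their imaging is timed from randomization: Q8W through Week 49, then Q12W. Assume the time of stopping is spread evenly over the imaging cycle, and ignore visit windows.
- Q8W (56-day cycle): a 60-day gap always contains a visit; a 53-day gap misses one with probability (56 − 53)/56 = 5%.
- Q12W (84-day cycle): no visit falls in the gap for (84 − 60)/84 = 29% to (84 − 53)/84 = 37%.

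Some of these participants are therefore also asked only after day 90. But their late visit carries an AE-monitoring mark, and the survival contact does not.

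**The case against.** The best defense is that the duty to collect exists whatever the SoA marks.
- Section 7.1 requires data on clinical events to be collected after study drug stops, and Section 8.4 makes investigators responsible for detecting and reporting SAEs.
- The 90-day limit concerns when an event occurs, not when it is asked about. Survival follow-up may use medical record review, which can find an earlier admission.
- A related SAE that comes to the investigator's attention is reportable without time limit (8.4.1, Table 5), and deaths are captured through survival follow-up.

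All of this stands. It confines the likely loss to non-fatal SAEs, mainly those judged unrelated. It does not supply the missing prompt. Nor do the ad hoc sponsor requests, which concern survival status, or the Norwegian day-56 visit, which is a pregnancy test for women of childbearing potential on everolimus.

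Four stronger readings are tempting, and the documents do not support them.
- **That sites are excused from asking.** A reader might cite the sentence in Section 8.4.1 on former study participants. The sentence after it speaks of participants discharged from the study, whereas Section 7.1 says that stopping study drug is not withdrawal. People in survival follow-up are still in the study. Likewise, footnote c says what status information includes; it does not say that nothing else may be asked.
- **That the SAE comparison between arms is biased.** If belzutifan delays progression, the mix of stopping reasons might differ by arm. But neither document gives that mix, no missed-event rate can be derived, and the Tier 2 intervals are expressly descriptive.
- **That belzutifan-caused hypoxia or anemia is being missed.** The mean steady-state half-life in Section 2.2.6 is 15.4 hours, so five half-lives are 77 hours, or about 3 days. The safety visit at day 30 already includes pulse oximetry and hematology.
- **That the new-therapy clause is an error.** Read literally, therapy started on day 60 closes the window back at day 30. The clause is nevertheless used consistently for SAEs and hospitalizations in the SoA and Sections 4.1, 8.4.1 and 8.10. Changing it would be a policy choice.

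**Conclusion.** The point holds as a gap between a stated collection requirement and the schedule meant to deliver it. For participants who stop at BICR-verified progression and start no new anticancer therapy, 53 to 60 of the 90 days (59 to 67%) have no SoA-specified SAE or hospitalization prompt. The next contact, at day 107 to 128, has none either.

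The days follow directly from the protocol's offsets under the assumptions listed above. The number of participants does not: neither the share stopping at verified progression nor the share still without new therapy at day 90 is given, so no count of people or missed events is offered. The consequence is possible under-collection of non-fatal off-treatment SAEs and hospitalizations. No primary or key secondary hypothesis is touched. The correction is worth making because it is cheap and a mandated safety window otherwise depends on spontaneous report.

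**What to change.** In the SoA and Section 8.11.3.3, for participants not entering imaging follow-up:
1. Mark AE monitoring at the first survival contact. Have it ask about SAEs, serious ECIs, hospitalizations and emergency department visits since the Safety Follow-up Visit, through day 90.
2. Preferably, schedule that existing contact at day 90 (+7) after the last dose instead of 12 weeks after the safety visit. The look-back then covers 90 − 37 = 53 to 97 − 30 = 67 days, against 84 − 7 = 77 to 84 + 7 = 91 days now.

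The first step alone supplies the missing prompt; the second shortens recall. The new-therapy clause can stay as it is.

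Cost: edits to the SoA and one section, an earlier telephone or record-review contact, and slightly more off-treatment SAE reporting. No visit, procedure or staff is added. At Amendment 09 the benefit falls mainly on participants not yet past day 90.
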